1.0 PROTOCOL SUMMARY AND/OR SCHEMA

We will perform a pilot study of serial [¹⁸F] 3'-deoxy-3'-fluorothymidine (FLT) PET imaging of the brain at baseline (less than 4 weeks of initiation of WBRT), up to 7-10 days post-treatment and 10-12 weeks after treatment in patients with metastatic breast cancer to the brain (N=20) treated with standard whole brain radiotherapy (WBRT) with or without sorafenib to evaluate the radiographic response to WBRT and sorafenib. We will examine if FLT- PET imaging can be used to determine early treatment response to sorafenib. Lastly, we will also assess whether FLT can distinguish residual viable tumor from inflammation or radionecrosis. This exploratory study will include two cohorts with 10 patients each. Cohort 1 will include the first ten patients treated with WBRT concomitantly with sorafenib (The first 10 patients on [name] I "Whole Brain Radiotherapy (WBRT) with Sorafenib for Breast Cancer Brain Metastases (BCBM): A Phase I Study" will also be enrolled concurrently on this trial). Cohort 2 will include patients treated with standard WBRT alone. Patients in both cohorts will also be assessed with standard non-invasive MRI imaging of the brain in addition to [¹⁸F] FLT PET at baseline and then 10-12 weeks after completion of WBRT. MR imaging will include T1 perfusion sequence (DCE- Dynamic Contrast enhanced Perfusion MR) images. Patients will later be followed with MR imaging of the brain every 3 months (+/- 7 days) during the first year, every 6 months (+/- 7 days) thereafter until CNS progression or death. FLT PET is considered investigational, and thus these scans will be performed under an FDA-approved Investigational New Drug (IND) application. The results of the FLT scans will have no impact on patient management. On 3/26/2009 an IND (#104742) was approved for the fluorothymidine (FLT). We will cross file this IND for the use of FLT in this protocol.

Schema:

* MRI will be done within one week before FLT PET scan

2.1 OBJECTIVES AND SCIENTIFIC AIMS

Primary Objective: The primary objectives of this study are as follows:

- 1) To examine the radiographic response to WBRT by FLT-PET and MRI for each cohort of 10 patients separately.
- 2) To examine and quantify changes in response as assessed by serial FLT PET images taken over the course of treatment for each cohort of 10 patients separately.

Secondary Objectives: The secondary objectives of this study are as follows:

- 1) To correlate treatment response as measured by FLT-PET with response assessment based on MRI of the brain in all patients and assess duration of response (i.e., CNS progression-free survival) during follow-up with MR imaging.

Exploratory Objective: The exploratory objectives of this study are as follows:

- 1) To correlate the ability of FLT-PET and MRI of the brain imaging to differentiate viable tumor, inflammation and necrosis with surgical resection specimens (if available) obtained in patients with a medical indication for craniotomy.

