12.3 Criteria for current objective status

At each tumor assessment visit the current objective status is determined. This takes into account measurable and evaluable lesion(s). Comparisons of assessments for measurable and evaluable lesions, excluding progressive disease, are based upon major changes in tumor size on Gd-MRI scan compared to the baseline scan. The assessment is adapted from Macdonald et al. Determination of progressive disease is based upon comparison to the previous scan with the smallest measurements. Scan changes are emphasized, but are interpreted in light of steroid use and to a lesser extent, neurological findings. Categories of overall response include:

Complete response (CR): Disappearance of all enhancing tumor on consecutive MRI scans at least one month apart, off steroids and neurologically stable or improved. No new lesions may arise.

Partial response (PR): Greater than or equal to a 50% reduction (< 100%) in the sum of the products of the largest perpendicular diameters of contrast enhancement for measurable lesions and if an evaluable lesion(s) is present at baseline, no worsening for an evaluable lesion(s) on consecutive Gd-MRI scans at least one month apart, steroids stable for 72 hours prior to each scan at the same dose administered at the time of the previous scan or at a reduced dose, and neurologically stable or improved. No new lesions may arise.

Progressive disease (PD): Greater than or equal to a 25% increase in size of the product of the largest perpendicular diameters of contrast enhancement for any measurable lesions or if an evaluable(s) lesion is present at baseline, worsening for an evaluable lesion(s) or any new tumor on Gd-MRI scans or greater than or equal to 25% increase in the unidimensional measurement of the any lesion in an additional plane of axis, steroids are stable for 72 hours prior to each scan at the same dose administered at the time of the previous scan or at an increased dose, with or without neurological progression. The following will also apply:

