Unknown (UNK): If any measurable or evaluable lesions have not been assessed or the assessment was made using a technically inferior method compared to baseline, the current objective status is “unknown”, even if the bulk of disease was evaluated. An exception would be if the objective status is PD because either a new lesion was detected, evaluable disease clearly worsened or the remaining lesions classify for a PD even without the lesions which were not assessed, i.e. the sum of all lesions which can still be measured show an increase of more than 25% over the smallest sum of all measurable lesions which were present at baseline.

Stable disease (SD): All other situations.

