12.4.1 Determination of best response

The best response for each patient is determined from the sequence of objective statuses according to the following rules:

CR = at least two determinations of CR a minimum of 4 weeks apart before progression, preceded by lower statuses, or preceded, separated or followed by unknown statuses.

PR = at least two determinations of PR or better a minimum of 4 weeks apart before progression (but not qualifying for CR), preceded by lower statuses, or preceded, separated or followed by UNK statuses.

SD = at least one determination of stable disease or better

PD = a determination of progression in one of the first two assessments

UNK = the status is UNK only if all assessments before progression are UNK.

If there is a defined objective that includes the assessment/measurement of therapeutic response to the defined treatment intervention, then detailed description of the measure, methods to be used (e.g., scales and/or definitions to assess response) and the criteria to determine each level of therapeutic response should be included.

FLT-PET

Response assessment for FLT-PET will be as follows:

SUV max and average (42% threshold) for brain lesions will be measured (for FLT using summed images 45-60min). In addition, we will explore other measures such as metabolic tumor volume. For comparison, activity will also be measured in remote normal cortex and white matter. Tumor - to-normal ratios will be computed. Treatment induced changes in these parameters will be expressed as % decrease in radiotracer uptake. Tentatively, a decline by 25% [26] will be considered significant.

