As written in Section 10.1, FLT-PET imaging provides assessments in addition to SUV. These additional assessments are kinetic rate constants based on a compartmental model. These parameters will also be analyzed using the approach described above (median, mean, min and max summarize at each timepoint for each cohort). .

Based on these analyses, we will explore whether treatment response for the two modalities correlate To compare the two modalities, the proportion of patients with significant change in SUV (FLT-PET) as a dichotomous variable, will be calculated in the following two MRI response groups: CR+PR vs. PD+SD. The McNemar's test for paired samples will be done to test the agreement of the two modalities. In addition, boxplots of SUV will be graphed for each MRI response category for each cohort. Based on the literature in this patient population, there is a 65-70 percent response rate as per MRI. Median duration of response will be calculated and summarized overall and for each cohort separately.

Any clinical, tissue, or other correlations are entirely exploratory in nature. It is expected that 2 patients will be accrued per month, with accrual for all 20 patients taking approximately 1 year.

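### The FLT–MRI comparison sets an MRI response that carries steroid and neurological conditions against an FLT response that carries none; a scan-only MRI table should be added beside it

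*Combined protocol and SAP*

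**What the plan says.** **Objective (Section 2.1).** Secondary objective 1 is stated as "To correlate treatment response as measured by FLT-PET with response assessment based on MRI of the brain in all patients".

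**MRI response (Section 12.3).** Complete response is defined as "Disappearance of all enhancing tumor on consecutive MRI scans at least one month apart, off steroids and neurologically stable or improved". Partial response starts from "Greater than or equal to a 50% reduction (< 100%) in the sum of the products" of lesion diameters. It also requires no worsening of evaluable lesions, no new lesion and confirmation on consecutive scans. The steroid dose must be stable for 72 hours before each scan, "at the same dose administered at the time of the previous scan or at a reduced dose, and neurologically stable or improved". Whatever is not complete response, partial response, progression or unknown goes to the residual category: "Stable disease (SD): All other situations". The section introduces these rules with the remark "Scan changes are emphasized, but are interpreted in light of steroid use and to a lesser extent, neurological findings".

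**FLT response (end of Section 12.4.1, and Section 14).** The rule is a fall in uptake: "Tentatively, a decline by 25% [26] will be considered significant". Section 14 applies it to SUVmax. Neither place attaches a steroid, neurological or confirmation condition.

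**Comparison (Section 14).** Here the plan is that "the proportion of patients with significant change in SUV (FLT-PET) as a dichotomous variable, will be calculated in the following two MRI response groups", the groups being CR+PR and PD+SD. McNemar's test is then used to assess agreement, and boxplots of SUV are drawn by MRI category. No MRI classification based on the scan alone is planned, and no sensitivity analysis.

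**The concern.** The objective asks whether two imaging methods tell the same story. One of the two variables also contains steroid use and neurological status, and the other does not. Take a patient whose lesions shrink by 60% and whose SUV falls by 60%, but who takes more steroid at the 10–12 week MRI than at baseline. That patient is MRI stable disease and an FLT responder: a discordant pair, although the scans agree.

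Read literally, the complete-response wording extends this. If all enhancement disappears while the patient is still on steroids, complete response fails because steroids have not been stopped. Partial response fails because the reduction is not below 100%. The case defaults to stable disease.

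At stake is the interpretation of the FLT-responder/MRI-nonresponder cell. Section 3.5 hypothesises that FLT-PET is the more accurate biomarker, so an excess in that cell could be credited to FLT when part of it comes from the clinical conditions.

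**Working it through.** The plan gives no power, alpha or precision figure for this comparison, so there is nothing of its own to reproduce. The check has two parts.

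**1. Direction, from the definitions.** Classify patients by scan change alone, with cell probabilities a (FLT+/MRI+), b (FLT+/MRI−), c (FLT−/MRI+) and d (both negative). Let a share s of MRI size responders fail a steroid or neurological condition, regardless of FLT result.

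- FLT+/MRI− becomes b + a·s.
- FLT−/MRI+ becomes c·(1 − s).
- The difference that McNemar's test examines becomes (b − c) + s·(a + c), so it can only move towards FLT.
- Total discordance changes by s·(a − c). If the blocked share differs by FLT result, the change is s₁·a − s₂·c, which can have either sign: a blocked FLT−/MRI+ patient becomes a concordant nonresponder. Raw agreement therefore has no fixed direction.
- The steroid condition in the progression rule cannot offset this. A patient who fails it becomes stable disease, which is in the same pooled group as progression.

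**2. Size, as an illustration only.** Inputs: N = 20 (Section 14); size-response rate r = 0.65–0.70, borrowed from the MRI response rate in Section 14; perfect scan agreement (b = c = 0), assumed; s = 10–30%, assumed because the documents give no figure.

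- Expected forced FLT+/MRI− pairs = 20·r·s.
- Observed MRI response = r(1 − s).
- Kappa = (pₒ − pₑ)/(1 − pₑ), with pₒ = 1 − rs and pₑ = r·r(1 − s) + (1 − r)(1 − r(1 − s)).
- Example, r = 0.70 and s = 0.20: pₒ = 0.86; pₑ = 0.70×0.56 + 0.30×0.44 = 0.524; kappa = 0.336/0.476 = 0.71.
- Exact two-sided McNemar with all pairs in one cell: p = 2×0.5ⁿ, so five pairs give 0.0625 and six give 0.031. The plan states neither alpha nor sidedness; two-sided 0.05 is assumed. The chance of six or more comes from Binomial(20, rs).

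| s | Forced pairs | Observed MRI response | Kappa | P(six or more pairs) |
|---|---|---|---|---|
| 10% | 1.3–1.4 | 58.5–63% | 0.86–0.84 | 0.1–0.2% |
| 20% | 2.6–2.8 | 52–56% | 0.74–0.71 | 4–5% |
| 30% | 3.9–4.2 | 45.5–49% | 0.62–0.58 | 18–23% |

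With some random scan disagreement as well (b = c = 0.10, r = 0.675, so a = 0.575) and s = 20%, expected FLT+/MRI− pairs rise from 2.0 to 20×(0.10 + 0.575×0.20) = 4.3. FLT−/MRI+ pairs fall from 2.0 to 20×0.10×0.80 = 1.6. The chance that the exact test rejects rises from 0.5% to 7.9%.

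**Check on r.** Section 14 describes 65–70% as the response rate by MRI, not as a size-only rate. If it already includes the clinical conditions, the size rate is r/(1 − s). That is 0.65/0.9 to 0.70/0.9 = 72–78% at s = 10%, and 93–100% at s = 30%. At s = 40% it would be 108–117%, which is impossible, so the illustration stops at 30%.

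**The case against.** The strongest reply is that this is a choice and not a mistake. Section 12 adopts an established composite criterion, and the objective speaks of response assessment based on MRI, not of lesion size. Steroids alter how shrinkage should be read, so a size-only comparator brings in a distortion of its own. This stands. A reader might infer that the composite is wrong for this comparison and should be replaced; the documents do not support that, and the composite should stay.

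A reader might also infer that the whole FLT–MRI comparison is biased one way. Only the marginal comparison has a fixed direction, as shown above.

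A third tempting inference is that the artefact differs between cohorts because sorafenib reduces edema. Section 3.5 says only that it could, the step from edema to steroid dose is not in the plan, and Section 14 plans no between-cohort test of concordance.

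Other asymmetries may matter as much. The FLT threshold is 25% and the MRI threshold 50%, and only MRI response needs confirmation, although one post-WBRT MRI falls in the 10–12 week window. The illustration sets both aside. The stakes are also limited: this is a descriptive pilot, FLT results do not affect management, and no decision rests on McNemar's test.

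The remark that scan changes are emphasized, and the shorter description of complete response in Section 12.2, might lead an assessor to relax the conditions. They do not remove them from the Section 12.3 definitions. The calendars in Section 10.2 and Appendix A schedule no steroid record or neurological examination after screening, so how the conditions would be applied is unclear.

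**Conclusion.** The concern holds in a limited form. By the plan's own definitions, agreeing scans can be scored FLT responder/MRI nonresponder, and in the McNemar comparison the effect can only lower MRI response relative to FLT. Its size cannot be determined from the documents. Under the stated assumptions it is one to three pairs in 20 at s of 10–20%, where a falsely significant exact test is uncommon (at most about 5%). It is about four pairs at 30%, where the chance is 18–23%. These figures isolate one mechanism; they do not estimate this study's bias, and a reader should not infer that a spurious significant result is likely. A few such pairs can still alter the reading of a 20-patient table. This is a modest improvement to a secondary objective in a pilot study.

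**What to change.** In Section 14, keep the CR+PR versus PD+SD comparison based on Section 12.3. Add the same table, McNemar test and boxplots with a scan-only MRI classification at the 10–12 week MRI:

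- Keep every imaging element of Section 12.3: at least a 50% fall in the sum of products or disappearance of all enhancement; no growth of 25% or more in any measurable lesion; no worsening of evaluable lesions; no new lesion.
- Leave out only the steroid and neurological conditions.
- State that this is a single-scan, unconfirmed status, because only one post-WBRT MRI falls in that window. Where the Section 12.3 status relies on confirmation, say so, since that can also move a patient between the tables.
- Report how many discordant pairs change between the two tables, and attribute FLT–MRI discordance to the modalities only if it persists in the scan-only table.

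Leave Section 12.3 unchanged for the MRI response distribution and CNS progression-free survival.

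The cost is a paragraph of analysis wording and one further set of outputs, using diameters already recorded under Section 12.1; no new scans are needed. The downsides are that two MRI variables are reported, the scan-only one can include steroid-assisted shrinkage, and the gap between the 25% and 50% thresholds remains.

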3.0 BACKGROUND AND RATIONALE

3.1 Brain metastasis from breast cancer

Brain metastasis affects 10-30% of women with metastatic breast cancer depending on subtype of breast cancer. The incidence of brain metastases appears to be rising as a result of superior imaging modalities, earlier detection, and more effective treatment of systemic disease. Survival remains poor despite treatment modalities like surgical resection and whole brain radiotherapy (WBRT). Prognosis depends largely on brain metastases recursive partitioning analysis (RPA) of Radiation Therapy Oncology Group prognostic class I to III (Table 1) [1,2] and biologic subtypes (Table 2) [3-5]. Effective treatment of brain metastases in these patients remains an unmet medical need.

Table 1: Recursive Partitioning Analysis (RPA) for patients with breast cancer brain metastases

RPA Class	Description	Median survival
I	Age <65 KPS \geq 70 Controlled primary site, AND ... Absence of extracranial metastases.	7.1 months
II	KPS \geq 70, and one of the following ... Age \geq 65 Uncontrolled or synchronous primary, OR ... Presence of non-CNS metastases	4.2 months
III	KPS <70	2.3 months

Table 2. Prognosis by histologic subtypes

Subtype	PFS	OS
ER + [3,4]	4-6	6-7
HER-2 + [3,4]	12	10-22
Triple Negative (ER, PR and HER-2 negative) [3-5]	3.7	5

3.2 Treatment of brain metastases

Therapeutic approaches to brain metastases include surgery, WBRT, stereotactic radiosurgery, chemotherapy and more recently novel molecularly targeted therapy. Sorafenib is an oral anti vascular endothelial growth factor (VEGF) and multi- tyrosine kinase inhibitor with demonstrated safety and activity in various tumor types including breast cancer [6]. VEGF TKI have the potential for increased CNS penetration compared to VEGF monoclonal antibodies and recently, long lasting successful cerebral response of sorafenib has been reported in brain metastases [7].

3.3 Sorafenib and cranial radiation in the treatment of brain metastases

In preclinical models, radiation treatment followed sequentially by sorafenib was found to be associated with delay in tumor growth [8]. Sorafenib has been given safely with concurrent cranial radiation for brain metastases [9]. Ongoing studies are further evaluating the feasibility and activity of tyrosine kinase inhibitors in combination with cranial radiotherapy. We are currently conducting an open label phase I, standard 3+3 design, trial of sorafenib given concurrently with WBRT for patients with metastatic breast cancer to the brain. The first ten patients from this trial will have to agree and be enrolled on this study in addition to patients who receive standard WBRT for treatment of brain metastases from breast cancer.

3.4 [¹⁸F] FLT PET imaging

3'-deoxy-3'-[¹⁸F] fluorothymidine ([¹⁸F] FLT) is a new PET radiotracer that can be used to assess tumor cell proliferation [10]. FLT is a thymidine analog that tracks the salvage pathway of DNA synthesis, becoming phosphorylated by thymidine kinase 1 (TK1). FLT differs from thymidine in that it does not become incorporated into DNA; however phosphorylation by TK1 traps in the cell. TK-1 activity is up-regulated in cells entering the S-phase, whereas the protein is nearly undetectable in growth arrested cells. Thus, the uptake of FLT correlates with thymidine uptake, thymidine kinase activity, and the percentage of cells in S-phase. It can therefore be used to image and measure tumor proliferation in cells that predominantly use the salvage pathway.

Shields et al [11] published the first human studies using FLT-PET in a patient with non-small cell lung cancer, demonstrating the high image quality and low background afforded by FLT. Good images were obtained from injection of 5 mCi or less of FLT, and imaging stable

uptake was noted at around 45 to 60 minutes after injection. Recently, dosimetry data for FLT have been published [12], showing that patient imaging is feasible with clinically acceptable radiation exposure for the subject. This is a critical issue for FLT because it is likely to be used in clinical applications that require repeated studies to measure response to therapy. These studies paved the way for a series of pilot studies examining FLT-PET imaging for a variety of tumors. We elected to use an activity of up to 10 mCi per injection for the proposed dynamic imaging studies, based on dosimetry estimates (see section 11.2)

3.4.1 [¹⁸F] FLT PET imaging to image cellular proliferation and treatment response

Preclinical studies have identified the potential of FLT as a PET imaging agent for cellular proliferation. Cellular proliferation has a number of potential advantages over imaging with FDG-PET, particularly the low background activity of normal brain tissue in contrast to the high FDG uptake (glucose utilization) by normal brain tissue. In addition, FLT is expected to be more specific to malignant processes since high glucose metabolism, measured by FDG PET, is also seen in a variety of benign conditions, including inflammation and tissue healing. Changes in cellular proliferation occur early in response to treatment and proliferation imaging likely provides an earlier and more definitive assessment of response than imaging with FDG, which can be compounded by a variety of issues, including cellular repair. In the case of cytostatic agents, which stop cell division but not necessarily lead to cell death, tumor proliferation declines, but tumor energy metabolism may not change. All these considerations provide an impetus for PET cellular proliferation imaging, especially as a tool for measuring early response [13].

Although preclinical models demonstrate the potential utility of FLT-PET for measuring therapeutic response, limited data are available for this use in humans. Preliminary studies used FLT to monitor neoadjuvant breast cancer treatment and showed that FLT could measure changes early in the course of treatment [14]. Our own ongoing studies in large cell lymphoma confirm this. The appropriate clinical application of FLT is for characterizing known tumors and assessing their response to treatment through serial imaging studies.

Most early series focused on testing the feasibility of FLT-PET imaging and comparing FLT uptake with in vitro measures of tumor proliferation, typically the Ki-67 (MIB-1) index. Some studies also compared FLT-PET with FDG-PET, given the established clinical role of FDG for staging in the tumor types studied. Studies have shown good correlation between FLT uptake and the Ki-67 index for a variety of tumors [15, 16]. In cases where FDG-PET was also performed, the correlation for FLT uptake versus Ki-67 index was much better than the correlation for FDG uptake versus Ki-67. In one study, when FLT-PET was compared side to side with FDG-PET in 25 patients with newly diagnosed or previously treated gliomas, it was found that FLT- PET was more sensitive to FDG-PET to image recurrent high-grade gliomas, correlated better with Ki-67 values and was a more powerful predictor of tumor progression and survival [17].

[¹⁸F] FLT PET imaging of the brain has been used by the University of Washington, Wayne State University, UCLA, MSKCC, and others to image proliferation.

3.4.2 [¹⁸F] FLT PET imaging and MR imaging of the brain

It is difficult to distinguish between genuine tumor progression and radionecrosis using conventional gadolinium MRI imaging or FDG-PET imaging of the brain [18 - 20]. To enable improved discrimination of radionecrosis versus progression of disease, fluoro-L-thymidine (FLT)-PET imaging may be useful as it allows for a noninvasive assessment of cell proliferation *in vivo*, a key feature of malignancy.

